Aim 1. Determine the effect of sleep extension on whole-body, multi-organ and cellular metabolic function in MU adults. We hypothesize that sleep extension implemented at home in people who chronically maintain short sleep schedules will: i) improve *in vivo* insulin sensitivity in the liver, adipose tissue and muscle; ii) have beneficial effects on 24h plasma insulin (concentration, secretion and clearance) glucose, and FFA profiles; iii) decrease intrahepatic triglyceride content; and iv) alter specific plasma metabolites (assessed every 6h for 24h) that are known to be associated with insulin resistance and the development of T2D.

In addition, untargeted metabolomics analyses will be performed to help identify novel metabolites associated with sleep extension-induced improvement in metabolic function that will serve as the basis for future investigation of these specific metabolites/bioactives.

Aim 2. Determine the effect of sleep extension on purported mechanisms responsible for metabolic dysfunction induced by obesity or sleep restriction: i) misalignment between the master clock of the suprachiasmatic nucleus (assessed by 24h plasma melatonin rhythm) and peripheral circadian clocks (assessed by serial measurements of peripheral blood mononuclear cell [PBMC] gene expression); ii) oxidative stress (urinary 8-iso-prostane F2 α , plasma oxysterols and glutathione-to-oxidized glutathione ratio, and adipose tissue protein carbonylation); and iii) systemic and adipose tissue inflammation (proinflammatory cytokines and prostanoids). We hypothesize that sleep extension will: i) improve alignment between central and peripheral rhythms; ii) reduce oxidative stress; and iii) decrease plasma and adipose tissue markers of inflammation.

We will test these hypotheses by: i) a one-stage hyperinsulinemic-euglycemic clamp (HEC) procedure plus stable isotope tracer infusions; ii) 24h urine collection iii) hourly blood sampling for 24h; iv) muscle and adipose tissue biopsies; and v) magnetic resonance imaging.

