D2.1. Study flow and overview. A randomized, controlled trial will be conducted in MU people to evaluate the effect of 4-6 wk of sleep extension (to account for the time needed to complete follow-up testing) on metabolic function, circadian biology, inflammation and oxidative stress (Fig. 4). A 4-6 wk duration of sleep extension was chosen because a decrease in fasting plasma insulin concentration has been reported after 6 wk of sleep extension in healthy, non-obese subjects⁴⁸. A randomized, cross-over study design (i.e. participants randomized to habitual short sleep or to extended sleep and then cross-over to the other condition) is not being done because of the concern that subjects would find that extending their sleep was beneficial and would not go back to their previous short sleep pattern. Indeed, in our previous sleep extension study (see preliminary data in section C2.5), subjects who extended their sleep completed a 3-wk post-study sleep log which showed they continued to sleep more than 7h per night by their own choice.

Fig. 4. Study overview

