Metabolomics. State-of-the-art mass spectrometry techniques will be used to measure specific circulating metabolites that have been linked with metabolic dysfunction and/or sleep restriction, including markers of inflammation, oxidative stress, and insulin resistance (see section **D2.2.1**). These metabolites will be evaluated in blood samples obtained every 6h for 24h to provide an integrated assessment of plasma concentrations throughout the day. Additionally, we will measure a key marker of oxidative stress in a 24h urine collection (urinary 8-iso-prostane F2 α)^{62,63}. To capture these metabolites of interest, multiple complementary LC methods will be performed as previously described^{62,63}, each optimized to capture a chemical subset of the metabolome, and coupled to a high resolution Thermo Orbitrap QExactive mass spectrometer. This orthogonal chromatography will include hydrophilic interaction liquid chromatography (HILIC) using a Sequent Zic-pHILIC HPLC column to capture polar metabolites, reverse phase chromatography using a superficially porous Phenomenex Kinetex C18 UPLC column to capture lipids and peptides, and weak ion exchange chromatography using a Phenomenex Luna aminopropyl HPLC column to capture sugars, nucleotides, and phosphates. Metabolites of interest are definitively identified by using MS/MS analysis, with matching of LC measures and MS/MS fingerprint to commercial metabolite standards. In addition to targeted measures, simultaneous untargeted metabolomics analyses will be performed to comprehensively identify novel metabolites that may be associated with sleep related improvement in metabolic function. These metabolite markers will serve as the basis for future investigation and potentially enable discovery of novel metabolite biomarkers and bioactives involved in improved metabolic function induced by sleep extension in persons with MUO.

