Molecular analyses. Total RNA will be isolated from PBMC, muscle and adipose tissue biopsy samples in Trizol reagent (Invitrogen, Carlsbad, CA) or RNeasy kit (Qiagen, Valencia, CA). Real time-PCR will be used to determine gene expression^{36,67,87,88}. Expression of clock genes (e.g. *CLOCK*, *BMAL1*, *PER1*, *PER2*, *CRY1*, *CRY2*, *REV-ERBa*, *DBP*) in PBMC and markers of inflammation (e.g. *IL6*, *TNF*, *CCL2*, *CD68*) and oxidative stress (e.g. *NQO1*, *DHCR24*, *UCHL1*)³⁶ in muscle and adipose tissue will be determined. Adipose tissue protein carbonylation will be evaluated with an OxyBlot Protein Oxidation Detection Kit (Millipore)¹¹¹.

Circadian Melatonin Phase Assessment. Blood samples from the 24h blood sampling studies will be used to measure melatonin concentrations to determine the Dim Light Melatonin Onset (DLMO) and the Dim Light Melatonin Offset (DLMOFF) (linear interpolation of 25% of the fitted peak to trough amplitude), as we have

done previously^{108,112-114}. We will also calculate the timing of the midpoint between the DLMO and DLMOFF. We considered other circadian phase markers (e.g. core body temperature and cortisol), but will use melatonin because it is the most precise and accurate marker of circadian phase in people¹¹⁵.

Calculation of substrate and hormone kinetics. Endogenous glucose and palmitate Ra into the circulation and glucose Rd will be calculated as we have previously described^{36,87}. The hepatic insulin sensitivity index will be calculated as the reciprocal of the product of endogenous glucose Ra and basal plasma insulin concentration¹¹⁶. The adipose tissue insulin resistance index will be calculated as the product of endogenous palmitate Ra and basal plasma insulin concentration¹¹⁷. Plasma substrate and hormone concentration areas-under-the-curve for 5 h after initiating meal consumption and for the entire 24h will be calculated by using the trapezoid method¹¹⁸. Insulin secretion will be estimated by C-peptide deconvolution during the 24h blood sampling study¹¹⁹ and insulin clearance rates by dividing the ISR AUC by the insulin AUC over each meal period and over the full 24h and by compartmental modelling during the HEC procedure¹²⁰.

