D4.1. Data analyses. Statistical evaluation of the study data will be conducted in collaboration with [name], a biostatistician in the Washington University Institute of Clinical and Translational Sciences (ICTS) Research Design & Biostatistics Group. We will use a modified intention-to-treat (mITT) analysis, in which all subjects that complete the study will be analyzed regardless of their adherence to the assigned sleep intervention (i.e., continued short sleeping pattern in the control group and successful sleep extension [adding ~2 h of time-in-bed per night ensuring at least 7h/night] in the sleep extension group). Analysis of covariance (ANCOVA) with the post-treatment value as the dependent variable will be used to determine whether there are between group differences in our metabolic outcomes assessed during the HEC procedure and 24-h blood sampling study with the pre-intervention value used as a covariate. Characteristics at baseline between groups will be compared by using t-tests or Wilcoxon's test for continuous variables and chi square tests for dichotomous variables; any significant differences between groups will be used to adjust subsequent statistical analyses when necessary. Violations of the assumption of homogeneity of variance and/or sphericity will be corrected, if necessary, via transformation of data to produce data that satisfy normality and equal variance assumptions^{90,121-123}. As this protocol incorporates a 2-time point, pre-post study design there is no basis to input follow-up data when only baseline data are available. Because of this limitation, we will compare characteristics between completers and non-completers by using t-tests or Wilcoxon's test for continuous variables and chi square tests for dichotomous variables; these results will be reported in addition to the ANCOVA analysis. Metabolite analyses will be performed by using an ANOVA and Tukey post-hoc testing for statistical significance between conditions and across time. For discovery based untargeted metabolomics analysis, a conservative statistical threshold will be applied at the outset (Bonferroni corrected P value of $<10^{-5}$ to account for multiple hypothesis testing). To further minimize false discovery, we will also use principal component analysis as well as sparse partial least squares and LASSO regression with internal cross-validation. Metabolites identified using these methods will be prioritized for future investigation as potential mechanisms underlying sleep related metabolic improvements.

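### Targeted metabolites (Aim 1(iv)) are given an ANOVA with Tukey tests that names no deciding term and no baseline covariate, and D4.1 does not say how this fits with its ANCOVA

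*Combined protocol and SAP*

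**What the plan says.** Aim 1(iv) in section A predicts that sleep extension will "alter specific plasma metabolites (assessed every 6h for 24h) that are known to be associated with insulin resistance". Section D2.5 (Metabolomics) describes a targeted set "including markers of inflammation, oxidative stress, and insulin resistance" and says of it: "These metabolites will be evaluated in blood samples obtained every 6h for 24h to provide an integrated assessment of plasma concentrations throughout the day". These samples come from the 24-h inpatient study in D2.2.1, which is done at baseline and repeated after the intervention (D2.4).

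D4.1 then contains two statements that can both apply to these data:

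- Between-group differences in metabolic outcomes from the clamp and the "24-h blood sampling study with the pre-intervention value used as a covariate" are tested by ANCOVA, with the post-treatment value as the dependent variable.
- Further on: "Metabolite analyses will be performed by using an ANOVA and Tukey post-hoc testing for statistical significance between conditions and across time".

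Other sentences bear on how the second statement should be read. D4.1 adds that "Violations of the assumption of homogeneity of variance and/or sphericity will be corrected", which points to a repeated-measures model. D2.1, when describing the cross-over design that was not adopted, speaks of "participants randomized to habitual short sleep or to extended sleep and then cross-over to the other condition", so a condition there means a sleep assignment. D4.1 also allows adjustment for baseline characteristics found to differ between groups, and D7.6 names menstrual phase as a covariate. Neither supplies the baseline value of the metabolite. Untargeted metabolomics has its own threshold in D4.1 and is outside this point.

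**The concern.** Aim 1(iv) is a stated hypothesis, but the plan does not fix which result would confirm it. An ANOVA with arm, visit and sampling time yields an arm main effect, an arm-by-visit interaction, interactions with clock time and a family of Tukey pairs. The between-arm difference in change is the arm-by-visit term. It is a difference of differences, so it is not one of the Tukey cell pairs; those are within-arm changes or single-visit arm differences. Leaving the term unnamed leaves the choice open until the data are in hand.

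The second cost is precision. A baseline value exists for every metabolite and would be used as a covariate if the ANCOVA applied. Under the ANOVA sentence as written, it is not. The same sentence may also reach the targeted inflammation and oxidative-stress metabolites of Aim 2, because D2.5 places them in the same targeted set.

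**Working it through.** There is no plan figure to reproduce: D4.2 gives no SD, effect size or power for the Aim 1(iv) metabolites.

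**Inputs**
- 25 per arm (D2.3).
- Two visits, pre and post (D4.1).
- Two-sided 5% level (D4.2).
- Assumed, because the documents do not give it: correlation r between the pre and post values of one 24-h summary per participant, taken as 0.5, 0.6, 0.7 and 0.8. Variance is set to 1 at each visit.

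**Standard error of the treatment effect, n per arm**
- ANCOVA: √[(2/n)(1 − r²)(1 + 1/(2n − 4))], df 2n − 3.
- Change, i.e. the arm-by-visit contrast (its one-df F is the square of this t): √[(2/n) × 2(1 − r)], df 2n − 2.
- Post-only arm difference: √(2/n), df 2n − 2.

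Apart from the small factor 1 + 1/46 = 1.022 at n = 25, the variance ratios are (1 − r²)/[2(1 − r)] = (1 + r)/2 for ANCOVA against change, and 1 − r² for ANCOVA against post-only.

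**Worked case, r = 0.5, n = 25**
- ANCOVA SE = √(0.08 × 0.75 × 1.022) = 0.248.
- Change SE = √(0.08 × 1.0) = 0.283.
- ANCOVA reaches 80% power at 0.71 SD (0.708 before rounding). The noncentrality is then 0.708/0.248 = 2.86 for ANCOVA and 0.708/0.283 = 2.50 for change, which gives 69% power for change.

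**All cases, noncentral t, effect set so that ANCOVA has 80% power**

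| r | Effect (SD) | ANCOVA variance below change | Power, change | Per arm for change to match | Power, post-only |
|---|---|---|---|---|---|
| 0.5 | 0.71 | 25% | 69% | 33 | 69% |
| 0.6 | 0.65 | 20% | 72% | 31 | 62% |
| 0.7 | 0.58 | 15% | 74% | 29 | 53% |
| 0.8 | 0.49 | 10% | 77% | 28 | 40% |

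The per-arm column is 25 divided by (1 + r)/2. With 22 completers per arm and the effect reset to 80% ANCOVA power, the ranges do not move (69-77% and 40-69%). The post-only column uses an ordinary 5% t-test, so it is generous to a Tukey-adjusted pair.

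**Simulation check.** 20,000 replicates, five samples per visit, trapezoid AUC, r of 0.5, 0.7 and 0.8. Power was 79.6-80.3% for ANCOVA, 69.0-76.6% for change and 39.4-69.0% for post-only. All three tests had size 4.8-5.2%.

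**The case against.** The strongest reply is that nothing essential is missing. The plan specifies an ANOVA and then Tukey tests, and in an arm-by-visit model the ANOVA's interaction F-test is exactly the between-arm difference in change. The ANCOVA sentence can also be read to cover these metabolites, since they come from the same sampling study and sit under Aim 1. Tukey would then only add time-of-day comparisons.

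Much of this stands. The interaction test is available and valid, so the gap is that it is not named and is less precise than ANCOVA. The ANCOVA reading is possible, but the later and more specific sentence prescribes another model for the same data, and nothing settles which prevails.

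Four stronger inferences are tempting, and the documents do not support them:
- *Repeated samples are treated as independent, so type I error is inflated.* The sphericity wording favours a repeated-measures model, under which error is correct.
- *The arms are never compared.* The use of the word condition in D2.1 makes a comparison of sleep assignments the natural reading.
- *Power may fall to 40%.* That needs a post-only comparison, the less likely reading, at the top of the assumed range of r.
- *A 24-h AUC is the required endpoint.* D2.5 defines one for substrates and hormones ("for the entire 24h will be calculated by using the trapezoid method") but does not prescribe it for these metabolites. If the six-hourly grid starts at the first sample (an assumption), the samples at 1, 7 and 13 h after waking coincide with the start of meals, and an AUC would then say little about post-meal responses.

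**Conclusion.** The point holds as a gap in specification with a moderate cost in precision. D4.1 does not name the term that tests Aim 1(iv), states no baseline covariate for it, and does not reconcile the ANOVA and ANCOVA sentences. On the repeated-measures reading, the supported loss is from 80% power to 69-77%, equivalent to needing 28-33 per arm instead of 25. These figures rest on the assumed correlation of 0.5 to 0.8, equal variances at the two visits and one 24-h summary per participant. The post-only range of 40-69% is a worst case under a less likely reading and should not be quoted as the expected loss.

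The primary outcome is not affected, and the Aim 1(iv) metabolites are not among the outcomes sized in D4.2. Two neighbouring matters are separate and should be settled on their own: multiplicity across the targeted markers, and the 3-hourly (D2.2.1) versus 6-hourly (Aim 1, D2.5) sampling statements.

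**What to change.** State in D4.1 that, for each targeted metabolite, Aim 1(iv) is tested by the between-arm difference at follow-up from the ANCOVA already described there. The covariates would be the same metabolite's baseline value and sex; sex is the stratification factor in D2.3, and the ANCOVA does not now name it. Apply this to one pre-specified 24-h summary, for example the mean or the AUC over the scheduled samples. Alternatively, use a baseline-adjusted mixed model with a participant effect and name its arm contrast. Keep ANOVA with Tukey across sampling times as a secondary analysis. Say whether the same rule covers the Aim 2 metabolites in the targeted set.

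If the ANCOVA was always meant to govern these metabolites, one sentence saying so, with the summary and covariates named, is enough.

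The cost is plan wording and modest programming, with no new samples. Time-of-day comparisons would no longer be the formal test, and a 24-h summary can miss an effect confined to one part of the day. If such an effect is expected, the relevant window should be pre-specified instead.

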Fig. 2. Circadian misalignment and inflammation

proposed in the current study. The increase in sleep opportunity increased total sleep time by 2.4h/night (from ~5.8h/night to 8.2h/night) (Table 1). In addition, duration of N1, N2 and REM sleep significantly increased (data not shown) without altering sleep latency (time it takes to fall asleep) or sleep efficiency (sleep time divided by total time in bed). *These findings demonstrate our ability to increase sleep duration in people with short sleep schedules.*

Table 1. Effect of 2-week sleep extension intervention on PSG measured sleep

	Maintain habitual insufficient sleep	Extension from habitual insufficient to sufficient sleep		
	Before	After	Before	After
Time in bed (min)	336.1 ± 15.5	361.4 ± 8.7	348.8 ± 10.5	492.0 ± 10.4 ^{a,b}
Total sleep Time (min)	322.2 ± 14.9	346.8 ± 9.5	329.3 ± 10.6	464.5 ± 10.0 ^{a,b}
Sleep latency (min)	2.9 ± 1.8	2.1 ± 1.2	3.8 ± 2.0	7.6 ± 1.2
Sleep efficiency (%)	95.7 ± 0.8	96.0 ± 0.5	94.5 ± 1.2	94.5 ± 0.9

Values are means ± SEM. ^aValue significantly different from baseline value; p<0.01;

^bValue significantly different from effect of insufficient sleep condition, p<0.01.

C2.6. Use of high throughput liquid chromatography mass spectrometry (LC-MS) for untargeted, discovery metabolomics analysis. The reliable analysis of thousands of metabolites in biological samples, and an insightful interpretation of these complex datasets is not trivial. For this reason, we are collaborating with [name] at UCSD, who has a productive track record in using mass spectrometry-based approaches for targeted and untargeted discovery metabolomics⁶¹⁻⁶⁴, and in analyzing complex datasets⁶¹⁻⁶⁶. We will use these innovative LC-MS and computational approaches to assay the human metabolome in plasma to provide insights into the effects of sleep restriction/extension on metabolite determinants of metabolic function.

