
D4.2. Sample size considerations. Using G*Power 3.1.9.2¹²⁴ we estimate that 15 participants/group will be required to detect *realistic and clinically meaningful effects of sleep extension* (based on data from our own studies evaluating weight loss or weight gain^{36,87,88} and to data from our own and other groups assessing the metabolic effect of sleep restriction^{17-19,24}) with >90% power using two-sided tests at the $\alpha=0.05$ level of significance in all primary and secondary outcomes listed below.

D4.2.1 Primary outcome

Insulin-mediated glucose Rd. We have found the average insulin-mediated glucose Rd during high-dose insulin infusion to be 59.1 $\mu\text{mol/kg FFM/min}$ in people with obesity with a day-to-day variability of 6.4 $\mu\text{mol/kg FFM/min}$ (mean \pm SD) ⁷⁶. Using this SD and assuming similar variance in the sleep restriction and extension groups, we estimate we will be able to detect a $\sim 7.9 \mu\text{mol/kg FFM/min}$ ($\sim 13\%$) difference between groups. This difference is smaller than the $\sim 20\%$ reduction in insulin-mediated glucose Rd observed after acute (1 to 7 d) sleep restriction^{17-19,24}.

D4.2.2 Secondary outcomes

24-h glucose area-under-the curve (AUC). We have found average 24h glucose AUC is 2650 mg/dl/24h in people with obesity with a day-to-day variability of $80 \pm 130 \text{ mg/dl/24h}$ (mean \pm SD). Using this SD and assuming similar variability in both groups, we estimate we will be able to detect a between group difference of $\sim 137 \text{ mg/dl/24h}$ ($\sim 5.2\%$). Five nights of sleep restriction increases average plasma glucose concentration by 11% over 10 h during the day¹²⁵. Two nights of sleep restriction increases postprandial breakfast plasma glucose AUC by 7.4% after breakfast¹²⁶.

24-h insulin AUC. We have found average 24-h insulin AUC is $818 \pm 333 \mu\text{U/ml/24h}$ in people with obesity with a day-to-day variability of $26 \pm 85 \mu\text{U/ml/24h}$ (mean \pm SD). Using this SD and assuming similar variability in both groups, we estimate we will be able to detect a between group difference of $\sim 90 \mu\text{U/ml/24h}$ ($\sim 11\%$). Five nights of sleep restriction increases average plasma insulin concentration by 29% over 10 h¹²⁵. Two nights of sleep restriction increases postprandial breakfast plasma insulin AUC by 52%¹²⁶.

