
D7.2 Facilities for conducting sleep studies. The PI ([name]) is Director of the Clinical Research Unit, which now houses a newly-constructed, state-of-the-art sleep laboratory that coordinates services (certified polysomnographic technicians and equipment maintenance) with the Washington University Sleep Medicine Center. The CRU sleep laboratory was designed with direct and comprehensive input from the Co-Is of this proposal, [name], [name] and [name]. The sleep laboratory is comprised of a 170 sq. ft. temperature-, sound- and light-controlled sleep study room which is equipped with a Compumedics Grael PSG/EEG system with video monitoring. A control room with a dedicated computer for PSG review and processing is located just outside the sleep study room. A sound-insulated, light-proof catheter portal passes from the control to the sleep study room which allows blood sampling without entering the room and infusion of tracers and hormones with the infusion pump located in the control room to eliminate infusion pump noise at the bedside. The sleep study room is connected via intercom to the control room and the CRU nurses station. A shared software license is available for off-site sleep scoring and two Alice PDx Portable sleep diagnostic systems (Philips Health) are available for off-site or home sleep monitoring.

D7.3 Compliance with sleep extension and attrition. We recognize the potential risk of attrition in this long duration sleep extension outpatient study. Therefore, we have developed a specific strategy to help ensure compliance with the sleep extension protocol that is described in section **D2.3**. Moreover, our Co-Is at UCB have shown that successful sleep extension is possible (see preliminary data in section **C2.5**) with good compliance and minimal drop-outs (only 1 of 15 subjects was not compliant with the sleep extension protocol and was removed from the study). In addition, the research coordinators who will be involved in the present proposal have demonstrated considerable success in retaining study participants in previous studies (>90%) that involved rigorous long-term lifestyle intervention (diet-induced weight loss and weight gain, and exercise training) with even more complex metabolic assessments e.g., 36,87,88,127,128.

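### The untargeted metabolomics plan sets a fixed 10^-5 cut-off without a feature count, and credits PCA, sparse PLS and LASSO with false-discovery control that they do not have

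*Combined protocol and SAP*

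**What the plan says.** Section D4.1 covers the untargeted analysis in four steps.

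- **Test.** Metabolites are analysed by ANOVA with Tukey post-hoc comparisons, between conditions and over time. The baseline-adjusted ANCOVA in the same section is specified for the clamp and 24-h blood sampling outcomes.
- **Cut-off.** "a conservative statistical threshold will be applied at the outset (Bonferroni corrected P value of" less than 10^-5, explained as allowance for multiple testing.
- **Added methods.** As a further reduction of false discovery, "we will also use principal component analysis as well as sparse partial least squares and LASSO regression with internal cross-validation".
- **Use.** "Metabolites identified using these methods will be prioritized for future investigation".

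The only guide to the number of tests is in section C2.6: "The reliable analysis of thousands of metabolites in biological samples". Section D4.2 gives power for insulin-mediated glucose Rd, the two 24-h AUCs and gene expression, and none for metabolomics. Section D2.3 randomises 25 per arm. Under section D4.1, "all subjects that complete the study will be analyzed regardless of their adherence to the assigned sleep intervention", so 25 per arm is an upper limit.

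**The concern.** Three things that decide the content of the metabolite list are left open or wrongly justified.

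1. The cut-off is not tied to a feature count, so its familywise error rate is unknown.
2. PCA, sparse PLS and LASSO are presented as protection against false discovery. PCA is unsupervised and tests nothing. Cross-validation in sparse PLS and LASSO tunes prediction error and does not bound the share of selected features that are false.
3. The plan does not say how the cut-off and these methods combine. Under a gate, only features below 10^-5 go forward; the later methods then add no stated error control. Under a union, a feature chosen by any method goes forward, and the list has no error control.

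Aim 1 offers these metabolites as the starting point for later studies. A list that misses many real signals, or mixes in selections with no known error rate, would misdirect that work.

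**Working it through.** **Inputs from the documents.** Cut-off 10^-5 (D4.1); thousands of metabolites (C2.6); 25 per arm (D2.3); past retention above 90% (D7.3), which suggests about 22 to 25 completers per arm; two-sided tests (D4.2, assumed to carry over).

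**Assumptions.** The documents give no metabolite effect, SD, pre-post correlation or feature count. I take a 1-SD effect as the reference and vary the rest. Features are treated as independent.

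**1. Method check on a figure in the plan.** Primary outcome: 7.9/6.4 = 1.23 SD, 15 per group, two-sided 0.05. Noncentral-t power is 90.4%, which reproduces the stated figure of more than 90%.

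**2. What 10^-5 corrects for.** 0.05/m = 10^-5 gives m = 5,000. Familywise error at a fixed 10^-5 is 1 - exp(-m x 10^-5):

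| Tests m (assumed) | Familywise error |
|---|---|
| 2,000 | 2.0% |
| 5,000 | 4.9% |
| 10,000 | 9.5% |

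**3. Unadjusted power at 10^-5.** With n per arm and effect d in SD units, the noncentrality is d x sqrt(n/2) on 2n - 2 degrees of freedom. For n = 25 and d = 1 it is sqrt(12.5) = 3.54, against a critical t of 4.94 on 48 df.

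| n per arm | Effect | Power |
|---|---|---|
| 25 | 0.8 SD | 3.1% |
| 25 | 1.0 SD | 10.9% |
| 25 | 1.23 SD (the Rd design effect) | 31% |
| 22 | 1.0 SD | 7.1% |

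With 25 per arm, 80% power needs 1.66 SD.

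**4. Effect of baseline adjustment.** If 1 SD is the unadjusted SD and the pre-post correlation is rho, the effect in residual SDs is 1/sqrt(1 - rho^2), on 47 df.

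| rho (assumed) | Effect in residual SD | Power at 10^-5 |
|---|---|---|
| 0.5 | 1.15 | 23% |
| 0.7 | 1.40 | 51% |
| 0.8 | 1.67 | 81% |

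**5. Benjamini-Hochberg at 5% against the fixed cut-off.** Simulated, 25 per arm, unadjusted:

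| Features | True effects | Effect | Found by BH | Found at 10^-5 |
|---|---|---|---|---|
| 2,000 | 50 | 1.0 SD | about 45% | 11% |
| 5,000 | 50 | 1.0 SD | about 32% | 11% |
| 2,000 | 20 | 0.8 SD | about 8-9% | 3-4% |
| 5,000 | 20 | 0.8 SD | about 5% | 3-4% |

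The ranges are simulation noise; the exact value at 10^-5 for 0.8 SD is 3.1%. Realised false discovery under Benjamini-Hochberg was about 4 to 5%.

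**6. LASSO without a gate.** In 30 simulated datasets with no true effect (25 per arm, 1,000 features, 10-fold cross-validation), LASSO selected at least one feature in 60%, with a mean of 10 selected over all runs. With 10 or 20 true 1-SD features, about 70% or 57% of the selected features were false. The null rate depends on tuning: in a separate 60-run check it was 53% with the minimum-error penalty and 30% with the one-standard-error rule.

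**The case against.** **The text may describe a gate.** The cut-off is applied at the start and the other methods follow as further narrowing. On that reading the list keeps Bonferroni control for up to about 5,000 tests, and step 6 does not describe the plan. This stands. A reader might infer that features chosen only by LASSO or sparse PLS bypass the cut-off, but the text does not establish that. What it supports is that the combination rule is missing.

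**The 11% rests on an assumed effect and an unadjusted test.** This also stands. An ANOVA between conditions and across time might use the baseline and the repeated samples, and step 4 shows how much that could matter. It is tempting to say that the plan misses nearly all real effects, but the documents give no metabolite effect size from which to conclude that. They also do not commit to baseline adjustment for metabolites.

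**The number 10^-5 is a reasonable, openly conservative choice.** It agrees with thousands of metabolites. Reading the wording as an already adjusted P value would demand a raw P of about 2 x 10^-9 (10^-5/5,000), but that strains loose phrasing. Multiplying the features by the sampling times to reach tens of thousands of tests is not supported either: section D2.5 describes the 6-hourly samples as giving an integrated picture of the day.

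**The analysis is exploratory.** This is correct and limits the consequence to the quality of the follow-up list.

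**Conclusion.** The point holds as a gap in specification plus one wrong justification. The cut-off has no stated feature count, the metabolite test is not baseline-adjusted as written, the combination rule is absent, and the claim that PCA, sparse PLS and LASSO reduce false discovery is unsupported under either reading.

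The cost in power depends on the assumptions. For a 1-SD effect at 10^-5 it is about 11% unadjusted with 25 per arm and 7% with 22, but 23% to 81% with baseline adjustment at correlations of 0.5 to 0.8. The advantage of Benjamini-Hochberg is large for many 1-SD effects and small for few 0.8-SD effects, where the sample size is the main limit. A reader might infer that a trial conclusion is at risk. It is not: the primary outcome and the powered secondary outcomes do not depend on this analysis.

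**What to change.** In section D4.1, replace the cut-off and selection sentences with the following:

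- One baseline-adjusted between-arm contrast for each feature that passes quality control, using each person's 24-h mean.
- Benjamini-Hochberg false discovery rate of 5% over the actual number of features, stated in the report, as the only route by which a metabolite is called identified.
- PCA for quality control only.
- Sparse PLS and LASSO for ranking features only, with all samples from one participant kept in the same cross-validation fold.
- Deletion of the statement that these methods reduce false discovery.

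The cost is a change of wording and a few lines of code, using samples already planned. The downside is that about 5% of declared features are expected to be false, which is acceptable for a list meant to guide later studies.
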